### 10.3.2. Definition of SAE

If an event is not an AE per definition above, then it cannot be an SAE even if serious conditions are met (e.g., hospitalization for signs/symptoms of the disease under study, death due to progression of disease).

#### **A SAE is defined as any untoward medical occurrence that, at any dose:**

- Results in death
- Is life-threatening

The term 'life-threatening' in the definition of 'serious' refers to an event in which the participant was at risk of death at the time of the event. It does not refer to an event, which hypothetically might have caused death, if it were more severe.

#### **Requires inpatient hospitalization or prolongation of existing hospitalization**

- In general, hospitalization signifies that the participant has been detained (usually involving at least an overnight stay) at the hospital or emergency ward for observation and/or treatment that would not have been appropriate in the physician's office or outpatient setting. Complications that occur during hospitalization are AEs. If a complication prolongs hospitalization or fulfils any other serious criteria, the event is serious. When in doubt as to whether "hospitalization" occurred or was necessary, the AE should be considered serious.
- Hospitalization for elective treatment of a pre-existing condition that did not worsen from baseline is not considered an AE.

#### **Results in persistent or significant disability/incapacity**

- The term disability means a substantial disruption of a person's ability to conduct normal life functions.
- This definition is not intended to include experiences of relatively minor medical significance such as uncomplicated headache, nausea, vomiting, diarrhoea,

influenza, and accidental trauma (e.g. sprained ankle) which may interfere with or prevent everyday life functions but do not constitute a substantial disruption.
Is a congenital anomaly/birth defect
Other situations:

Medical or scientific judgment should be exercised in deciding whether SAE reporting is appropriate in other situations such as important medical events that may not be immediately life-threatening or result in death or hospitalization but may jeopardize the participant or may require medical or surgical intervention to prevent one of the other outcomes listed in the above definition. These events should usually be considered serious.

Examples of such events include invasive or malignant cancers, intensive treatment in an emergency room or at home for allergic bronchospasm, blood dyscrasias or convulsions that do not result in hospitalization, or development of drug dependency or drug abuse.

### 10.3.3. Recording and Follow-Up of AE and SAE

AE and SAE Recording

When an AE/SAE occurs, it is the responsibility of the investigator to review all documentation (e.g. hospital progress notes, laboratory, and diagnostics reports) related to the event.

The investigator will then record all relevant AE/SAE information in the CRF.

It is not acceptable for the investigator to send photocopies of the participant's medical records to GSK in lieu of completion of the GSK /AE/SAE CRF page.

There may be instances when copies of medical records for certain cases are requested by GSK. In this case, all participant identifiers, with the exception of the participant number, will be redacted on the copies of the medical records before submission to GSK.

The investigator will attempt to establish a diagnosis of the event based on signs, symptoms, and/or other clinical information. Whenever possible, the diagnosis (not the individual signs/symptoms) will be documented as the AE/SAE.

Assessment of Intensity
The investigator will make an assessment of intensity for each AE and SAE reported during the study and assign it to 1 of the following categories: 

Mild: An event that is easily tolerated by the participant, causing minimal discomfort and not interfering with everyday activities.

Moderate: An event that causes sufficient discomfort and interferes with normal everyday activities.

- Severe: An event that prevents normal everyday activities. An AE that is assessed as severe should not be confused with an SAE. Severe is a category utilized for rating the intensity of an event; and both AE and SAE can be assessed as severe. An event is defined as 'serious' when it meets at least 1 of the predefined outcomes as described in the definition of an SAE, NOT when it is rated as severe.

### Assessment of Causality

- The investigator is obligated to assess the relationship between study intervention and each occurrence of each AE/SAE.
- A "reasonable possibility" of a relationship conveys that there are facts, evidence, and/or arguments to suggest a causal relationship, rather than a relationship cannot be ruled out.
- The investigator will use clinical judgment to determine the relationship.
- Alternative causes, such as underlying disease(s), concomitant therapy, and other risk factors, as well as the temporal relationship of the event to study intervention administration will be considered and investigated.
- The investigator will also consult the MSDS and Product label.
- For each AE/SAE, the investigator **must** document in the medical notes that he/she has reviewed the AE/SAE and has provided an assessment of causality.
- There may be situations in which an SAE has occurred and the investigator has minimal information to include in the initial report to GSK. However, **it is very important that the investigator always make an assessment of causality for every event before the initial transmission of the SAE data to GSK.**
- The investigator may change his/her opinion of causality in light of follow-up information and send an SAE follow-up report with the updated causality assessment.
- The causality assessment is one of the criteria used when determining regulatory reporting requirements.

### Follow-up of AE and SAE

- The investigator is obligated to perform or arrange for the conduct of supplemental measurements and/or evaluations as medically indicated or as requested by GSK to elucidate the nature and/or causality of the AE or SAE as fully as possible. This may include additional laboratory tests or investigations, histopathological examinations, or consultation with other health care professionals.
- If a participant dies during participation in the study or during a recognized follow-up period, the investigator will provide GSK with a copy of any post-mortem findings including histopathology.
- New or updated information will be recorded in the originally completed CRF.

- The investigator will submit any updated SAE data to GSK within 24 hours of receipt of the information.

#### 10.3.4. Reporting of SAE to GSK

##### SAE Reporting to GSK via Electronic Data Collection Tool

- The primary mechanism for reporting SAE to GSK will be the electronic data collection tool.
- If the electronic system is unavailable, then the site will use the paper SAE data collection tool (see next section) in order to report the event within 24 hours.
- The site will enter the SAE data into the electronic system as soon as it becomes available.
- The investigator or medically-qualified sub-investigator must show evidence within the eCRF (e.g., check review box, signature, etc.) of review and verification of the relationship of each SAE to IP/study participation (causality) within 72 hours of SAE entry into the eCRF.
- After the study is completed at a given site, the electronic data collection tool will be taken off-line to prevent the entry of new data or changes to existing data.
- If a site receives a report of a new SAE from a study participant or receives updated data on a previously reported SAE after the electronic data collection tool has been taken off-line, then the site can report this information on a paper SAE form (see next section) or contacts the medical monitor/SAE coordinator by telephone.
- Contacts for SAE reporting can be found in the SRM.

##### SAE Reporting to GSK via Paper CRF

- Facsimile transmission of the SAE paper CRF is the preferred method to transmit this information to the medical monitor or the SAE coordinator.
- In rare circumstances and in the absence of facsimile equipment, notification by telephone is acceptable with a copy of the SAE data collection tool sent by overnight mail or courier service.
- Initial notification via telephone does not replace the need for the investigator to complete and sign the SAE CRF pages within the designated reporting time frames.
- Contacts for SAE reporting can be found in the SRM.

## **10.4. Appendix 4: Contraceptive Guidance and Collection of Pregnancy Information**

### **10.4.1. Definitions:**

#### **Woman of Childbearing Potential (WOCBP)**

A woman is considered fertile following menarche and until becoming post-menopausal unless permanently sterile (see below).

If fertility is unclear (e.g., amenorrhea in adolescents or athletes) and a menstrual cycle cannot be confirmed before first administration of study intervention, additional evaluation should be considered.

#### **Women in the following categories are not considered WOCBP**

1. Premenarchal
2. Premenopausal female with 1 of the following:
  - Documented hysterectomy
  - Documented bilateral salpingectomy
  - Documented bilateral oophorectomy

For individuals with permanent infertility due to an alternate medical cause other than the above, (e.g., mullerian agenesis, androgen insensitivity), investigator discretion should be applied to determining study entry.

Note: Documentation can come from the site personnel's: review of the participant's medical records, medical examination, or medical history interview.

3. Postmenopausal female
  - A postmenopausal state is defined as no menses for 12 months without an alternative medical cause.
  - A high follicle stimulating hormone (FSH) level in the postmenopausal range may be used to confirm a postmenopausal state in women not using hormonal contraception or hormonal replacement therapy (HRT). However, in the absence of 12 months of amenorrhea, confirmation with more than one FSH measurement is required.
  - Females on HRT and whose menopausal status is in doubt will be required to use one of the non-estrogen hormonal highly effective contraception methods if they wish to continue their HRT during the study. Otherwise, they must discontinue HRT to allow confirmation of postmenopausal status before study enrolment.

#### 10.4.2. Contraception Guidance:

 
• CONTRACEPTIVESa ALLOWED DURING THE STUDY INCLUDE:
 

 
• Highly Effective Methodsb That Have Low User Dependency Failure rate of <1% per year when used consistently and correctly.
 

 
• Implantable progestogen-only hormone contraception associated with inhibition of ovulationc
 

 
• Intrauterine device (IUD)
 

 
• Intrauterine hormone-releasing system (IUS)c
 

 
• Bilateral tubal occlusion
 

 
• Azoospermic partner (vasectomized or due to a medical cause)           
Azoospermia is a highly effective contraceptive method provided that the partner is the sole sexual partner of the woman of childbearing potential and the absence of sperm has been confirmed. If not, an additional highly effective method of contraception should be used. Spermatogenesis cycle is approximately 90 days.
 
Note: documentation of azoospermia for a male participant can come from the site personnel's review of the participant's medical records, medical examination, or medical history interview.
 
 

 
• Highly Effective Methodsb That Are User Dependent Failure rate of <1% per year when used consistently and correctly.
 

 
• Combined (estrogen- and progestogen-containing) hormonal contraception associated with inhibition of ovulationc 
 
• oral
 
• intravaginal
 
• transdermal
 
• injectable
 
 
 

 
• Progestogen-only hormone contraception associated with inhibition of ovulationc 
 
• oral
 
• injectable
 
 
 


 
• Sexual abstinence           
Sexual abstinence is considered a highly effective method only if defined as refraining from heterosexual intercourse during the entire period of risk associated with the study intervention. The reliability of sexual abstinence needs to be evaluated in relation to the duration of the study and the preferred and usual lifestyle of the participant.
 
 

 
a. Contraceptive use by men or women should be consistent with local regulations regarding the use of contraceptive methods for those participating in clinical studies.
 
b. Failure rate of <1% per year when used consistently and correctly. Typical use failure rates differ from those when used consistently and correctly.
 
c. [Male condoms must be used in addition to hormonal contraception]. If locally required, in accordance with Clinical Trial Facilitation Group (CTFG) guidelines, acceptable contraceptive methods are limited to those which inhibit ovulation as the primary mode of action.
 

Note: Periodic abstinence (calendar, sympto-thermal, post-ovulation methods), withdrawal (coitus interruptus), spermicides only, and lactational amenorrhea method (LAM) are not acceptable methods of contraception. Male condom and female condom should not be used together (due to risk of failure from friction)

## 10.5. Appendix 5: Abbreviations and Trademarks

### LIST OF ABBREVIATIONS

AE	Adverse event
ALT	Alanine Aminotransferase
ANCOVA	Analysis of covariance
AUC	Area under the curve
BMI	Body mass index
CA	Competent Authority
CIOMS	Council for International Organizations of Medical Sciences
CONSORT	Consolidated Standards of Reporting Trials
CPMS	Clinical Pharmacology Modelling and Simulation
CSR	Clinical Study Report
DRC	Data review committee
EC	Ethics committee
ECG	Electrocardiogram
GCP	Good Clinical Practice
GCSP	Global Clinical Safety and Pharmacovigilance
GSK	GlaxoSmithKline
HBsAg	Hepatitis B surface antigen
hCG	Human chorionic gonadotropin
HIV	Human immunodeficiency virus
ICF	Informed consent form
IDM	Intradermal microdialysis
IDSL	Integrated Data Standards Library
IEC	Independent Ethics Committees
IRB	Institutional Review Boards
MMRM	Mixed effect model for repeat measurements
QTcF	QT interval corrected for heart rate according to Fridericia's formula
RAP	Reporting and analysis plan
SAE	Serious adverse event
SD	Standard deviation (SD)
SGOT	Serum Glutamic-Oxaloacetic Transaminase
SGPT	Serum Glutamic-Pyruvic Transaminase
SoA	Schedule of Activities
SP	Substance P
SRM	Study Reference Manual
ULN	Upper limit of normal
WCBP	Women of childbearing potential
WNCBP	Women of non-childbearing potential.

**Trademark Information**

Trademarks of the GlaxoSmithKline group of companies	Trademarks not owned by the GlaxoSmithKline group of companies
None	None

Version history

SAP Version	Approval Date	Protocol Version (Date) on which SAP is Based	Change	Rationale
SAP	01 Jul 2021	03-NOV-2020	Not Applicable	Original version

1. INTRODUCTION

- The purpose of this SAP is to describe the planned analyses and output to be included in the Clinical Study Report for study 213224 (Protocol 2019N419175_00).

1.1. Objectives and Endpoints

[figure not shown]
Part 1

Objectives	Endpoints
Primary	

 To characterise the wheal response over time following skin challenge with ascending concentrations of SP on a single day 	
 Wheal response during the 2 h post-challenge period area under the curve (AUC) at each concentration of SP
Secondary	

 To characterise the wheal response over time following skin challenge with ascending concentrations of SP on a single day 	
 Wheal response during the 2 h post-challenge period at each concentration of SP (including maximum observed wheal response, time to maximum observed wheal response, time of complete wheal response disappearance)

 To characterise the flare response over time following skin challenge with ascending concentrations of SP on a single day 	
 Flare response during the 2 h post-challenge period at each concentration of SP (including AUC, maximum observed flare response, time to maximum observed flare response, time of complete flare response disappearance)

 To evaluate the safety and tolerability of SP 	
 Incidence of Adverse Events (AE) and Serious Adverse Events (SAE) Incidence of findings of clinical important changes in: 
 vital signs laboratory safety data 12-lead electrocardiogram (ECG)

Part 2

Objectives	Endpoints
Primary	

 To compare the wheal response over time following skin challenge with ascending concentrations of SP on two days 	
 Wheal response during the 2 h post-challenge period (AUC) at each concentration of SP across 2 challenge days
Secondary	

 To characterise the wheal response over time following skin challenge with ascending concentrations of SP on two days 	
 Wheal response during the 2 h post-challenge period at each concentration of SP across 2 challenge days (including maximum observed wheal response, time to maximum observed wheal response, time of complete wheal response disappearance)

 To characterise the flare response over time following skin challenge with ascending concentrations of SP on two days 	
 Flare response during the 2 h post-challenge period at each concentration of SP across 2 challenge days (including AUC, maximum observed flare response, time to maximum observed flare response, time of complete flare response disappearance)

 To evaluate the safety and tolerability of SP 	
 Incidence of Adverse Events (AE) and Serious Adverse Events (SAE) Incidence of findings of clinical important changes in: 
 vital signs laboratory safety data 12-lead electrocardiogram (ECG)
Exploratory	

 To investigate the effect of intradermal SP challenges on local exploratory biomarkers of mast cell activation. 	
 Change in levels of exploratory biomarkers in skin during up to 2hr post challenge time at each of the 2 challenge days.

1.2. Study Design

Overview of Study Design and Key Features

Panel B: IDM measurement				Panel C: Biopsy sample
At least 2 h before baseline sampling	Within 1 h before SP challenge	SP challenge	Up to 2 h after challenge	

At the site of each SP injection (and saline control): placement of IDM tubing
 
At site of each SP injection (and saline control): pre-challenge IDM sample
 
Up to 4 intradermal injections of increasing SP concentrations
 
At site of each SP injection (and saline control): measurement of wheal and flare responses, and IDM sampling
				
SP challenge
 
2 intradermal injections of one of the SP concentrations
 
Skin biopsy at site of challenge
 
Plus 1 control biopsy from non-challenged skin

Design Features	
 This is an open label, single centre, 2-part, prospective enabling study of SP intradermal challenge in healthy participants. Parts 1 and 2 will run sequentially. Part 1 will include 1 challenge visit; Part 2 will include two challenge visits. All participants will attend the clinical unit for a screening visit within 28 days before their first or only challenge visit. Eligible participants will be enrolled into Part 1 or Part 2, based on their availability. In Part 1, participants will attend the unit as outpatients for 1 challenge visit. The duration of Part 1, including screening, is not expected to exceed 4 weeks for each participant. In Part 2, participants will attend the unit as outpatients for 2 challenge visits and have 1 follow-up phone call; the timing of visits will be decided based on emerging data. The duration of Part 2, including screening and follow-up is not expected to exceed 7 weeks for each participant. At each challenge visit, up to 4 concentrations of SP will be assessed. Wheal and flare responses will be assessed after each challenge (parts 1 and 2) In part 2, participants will receive up to 6 additional SP intradermal injections for biomarker analysis: 
 IDM challenges: 4 increasing concentrations of SP (the same concentrations as those administered in the wheal and flare challenges); IDM samples will be taken at the site of each challenge, before and after challenge. Biopsy challenges at Challenge Visit 2: 2 at the same concentration of SP; 3 biopsies would be taken – one from each challenged site and one from a non-challenge area of skin. (these challenges and biopsies may or may not be performed, based on review of ongoing data.) Biomarker blood samples will be taken before the first SP challenge and after the last SP challenge at Challenge Visit 2. 			

Overview of Study Design and Key Features	
Study intervention	
At each challenge visit, up to 4 concentrations of SP will be assessed, as follows:
 
In Parts 1 and 2:
 
 Participants will first receive saline, by intradermal injection, and histamine by skin prick, as negative and positive controls. 
 If the wheal responses immediately after the 20 min post challenge period do not meet the acceptable saline and histamine responses (as defined in the SRM), the participant will not receive SP. If it happens in Part 1 or on Challenge Visit 1 in Part 2, the participant will be withdrawn from the study. If it happens on Challenge Visit 2 in Part 2 and if the participant marginally fails to meet the control criteria (as defined in the SRM), they may have the tests repeated. If they still fail to meet the control criteria, they will be withdrawn from the study. Following confirmation of acceptable control responses, participants will receive up to 4 intradermal injections of SP at different concentrations; injections will be given sequentially from lowest to highest concentration; wheal and flare responses will be assessed after each challenge. 
In Part 2 only:
 
 Participants will receive up to 6 additional SP intradermal injections for biomarker analysis
Study intervention Assignment	
 No randomization is planned Participants will receive up to 4 ascending SP concentrations
Data reviews	
 See Table 1

2. STATISTICAL HYPOTHESES

The objectives of this enabling study are to characterise the wheal and flare responses over time following skin challenges with ascending concentrations of SP. No formal hypotheses will be tested.

2.1. Multiplicity Adjustment

No multiplicity adjustment is planned here.

3. ANALYSIS SETS

Analysis Set	Definition / Criteria	Analyses Evaluated
Screened	
 All participants who signed the ICF and were screened for eligibility. 	
 Screen Failure
Enrolled	
 All participants in the Screened analysis set who entered the study. 
Note: screening failures (who never passed screening even if rescreened) and participants screened but never enrolled into the study (Met eligibility but not needed) are excluded from the Enrolled analysis set as they did not enter the study.
	
 Study Population
Safety	
 All participants in the Enrolled analysis set who received at least one challenge-related study procedure on their (first) challenge day 	
 Safety PD

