### Number of Participants:

Part 1 will enrol a sufficient number of participants to achieve up to 12 participants who have completed the challenge visit. Once Part 1 is complete, SP concentrations to be given in Part 2 will be confirmed. Part 2 will occur only if Part 1 is successful.

Part 2 will enrol a sufficient number of participants to achieve up to 20 participants who have completed the 2 challenge visits. The study may be stopped after review of data from about the first 10 participants.

Participants who withdraw or are withdrawn from the study may be replaced. In Part 2, following screening, replacement participants must start at Challenge Visit 1.

Participants may be enrolled into Part 1 or Part 2, not both. Therefore, the anticipated sample size is up to 32 participants (not including replacements).

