**At each challenge visit, up to 4 concentrations of SP will be assessed, as follows:**

- In Parts 1 and 2:
  - Participants will first receive saline, by intradermal injection, and histamine by skin prick, as negative and positive controls.
  - If the wheal responses within the 20 min after each control challenge do not meet the acceptable saline and histamine responses (as defined in the SRM), the participant will not receive SP.
    - If it happens in Part 1 or on Challenge Visit 1 in Part 2, the participant will be withdrawn from the study.
    - If it happens on Challenge Visit 2 in Part 2 and if the participant marginally fails to meet the control criteria (as defined in the SRM), they may have the tests repeated. If they still fail to meet the control criteria, they will be withdrawn from the study.
  - Following confirmation of acceptable control responses, participants will receive up to 4 intradermal injections of SP at different concentrations; injections will be given sequentially from lowest to highest concentration; wheal and flare responses will be assessed after each challenge.

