## 9.3. Populations for Analyses

The following populations are defined:

Population	Description
Screened	All participants who signed the ICF and were screened for eligibility.
Enrolled	All participants in the Screened population who entered the study
Safety	All participants in the Enrolled population who received at least one challenge-related study procedure on their (first) challenge day

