4.5. Safety Analyses

The safety analyses will be based on the Safety population. No formal statistical testing will be performed on safety data.

Displays will be generated for parts 1 and 2, separately (but in the same file) and for the study intervention group “Skin Challenges”.

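### If any participant fails the control challenges at the first challenge visit, the Safety set includes people never given SP and the SP-related adverse-event percentages for that Part are diluted

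*SAP*

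**What the plan says.** The safety objective in both Parts is "To evaluate the safety and tolerability of SP" (SAP 1.1).

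Protocol 4.1 fixes the order of challenges: "Participants will first receive saline, by intradermal injection, and histamine by skin prick, as negative and positive controls". If the control responses are not acceptable, "the participant will not receive SP". The consequence at the first or only challenge visit is stated: "If it happens in Part 1 or on Challenge Visit 1 in Part 2, the participant will be withdrawn from the study". SAP 1.2 repeats these rules. A repeat of the controls is offered only at Challenge Visit 2.

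The synopsis (Protocol 1.1, Number of Participants) adds: "Participants who withdraw or are withdrawn from the study may be replaced". Recruitment runs to a target number of completers.

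The Safety set in SAP section 3 is "All participants in the Enrolled analysis set who received at least one challenge-related study procedure on their (first) challenge day". Protocol 9.3 has the same rule: "All participants in the Enrolled population who received at least one challenge-related study procedure on their (first) challenge day". Neither requires an SP injection.

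SAP 4.5 states: "The safety analyses will be based on the Safety population". It shows each Part separately, under one intervention group named Skin Challenges. SAP 4.5.2 reports numbers and percentages of participants, and splits related AEs into those related to SP only, to histamine only, and to both. SP exposure itself appears only as a by-subject listing (SAP 4.5.1).

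**The concern.** The related-AE summaries have a numerator specific to the agent and a denominator that is not. A person who fails the controls at the first visit cannot have an event caused by SP, yet counts in the denominator of the SP-related percentages. Such failures are a planned route through the study, and because recruitment runs to a number of completers, they come on top of the participants given SP.

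At stake is whether the reported SP-related incidence describes people who received SP, as the objective requires. The same set underlies the laboratory, ECG and vital-sign summaries. Early-withdrawal assessments (Protocol 1.3.2) can enter the worst-case displays (SAP 6.2.4), so never-exposed participants may appear there too.

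**Working it through.** **The plan's own figure.** 12 (Part 1) + 20 (Part 2) = 32, the anticipated sample size without replacements in Protocol 1.1. It is stated not to rest on statistical considerations, so there is no power calculation to reproduce.

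**Is a first-visit control failure in the Safety set?**
1. The participant passed screening and came to the challenge visit. Protocol 4.1 says this person is withdrawn from the study, which implies having entered it, so the Enrolled definition is met.
2. Saline and histamine have been given, so a challenge-related procedure has been received on the first challenge day.
3. Both parts of the Safety definition are met, with no SP received.

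A failure at Challenge Visit 2 of Part 2 is different: that participant had SP at Visit 1 and is SP-exposed.

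**Size of the dilution.** Let N be the number given at least one SP injection, k the number of first-visit control failures in that Part, and x the number with an SP-attributed AE. The SP-exposed percentage is x/N. The planned percentage is x/(N+k). The ratio is N/(N+k).

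For x = 3 (assumed):

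| k | Part 1, N=12 | ratio | Part 2, N=20 | ratio |
|---|---|---|---|---|
| 0 | 25.0% | 1.00 | 15.0% | 1.00 |
| 1 | 23.1% | 0.92 | 14.3% | 0.95 |
| 2 | 21.4% | 0.86 | 13.6% | 0.91 |
| 3 | 20.0% | 0.80 | 13.0% | 0.87 |

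Both Parts may stop early (Protocol 9.5 and 1.1). With k=1, the ratio is 6/7 = 0.86 if Part 1 ends at about 6, and 10/11 = 0.91 if Part 2 ends at about 10.

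**By assumed failure rate f.** The number challenged is N/(1−f), rounded up.
- N=12: f = 5%, 10%, 20% gives 13, 14, 15 challenged; ratios 0.92, 0.86, 0.80.
- N=20: the same rates give 22, 23, 25 challenged; ratios 0.91, 0.87, 0.80.

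**Chance that the problem arises at all.** This is 1 − (1−f)^n for n challenged. For n = 12 and 20 it is 22% and 33% at f = 2%, 46% and 64% at 5%, and 72% and 88% at 10%.

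**Zero events.** The SAP plans no upper bound, but a reader might apply the one-sided 95% bound 1 − 0.05^(1/n). It is 22.1% for n=12 and 18.1% for n=15; for n=20 and n=25 it is 13.9% and 11.3%. The apparent gain comes from people not given SP.

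**Direction.** For events correctly attributed to SP, the ratio is below 1 whenever k ≥ 1. Two routes can reverse the direction:
- *Overall AE incidence.* A control failure can have a histamine, saline or procedure event. With 3 events in 12 SP-exposed participants and one control failure who has an event, the table shows 4/13 = 30.8% instead of 3/12 = 25.0%.
- *Missing relationship.* SAP 4.5.2 and 6.2.7 count a missing relationship as related. A never-exposed participant could then enter an SP-related numerator, with the same arithmetic.

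**The case against.** The strongest reply is that nothing may happen. Inclusion criterion 3 (Protocol 5.1) already requires a positive histamine and a negative saline response at screening, within 28 days of the first challenge. If nobody fails on the day, the Safety set and an SP-exposed set are identical. The acceptance limits are in the Study Reference Manual, so the failure rate cannot be judged from these documents. This stands, and it makes the point conditional.

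Second, the set fits its label. Saline, histamine and SP are all administered as part of the study intervention (Protocol 6.1), the display group is Skin Challenges, and a common denominator keeps the agent-specific tables comparable. This stands as a reason to keep the current set for all-challenge and histamine safety. It does not answer the objective, which names SP.

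Third, a reader could rebuild the rate from the AE counts, the exposure listing and the disposition table. Safety is descriptive, and the stopping rules in Protocol 7.1 use counts. The shift is also small against sampling error: 4/12 (33%) becomes 4/15 (27%) with k=3, while the exact 95% interval for 4/12 is about 10% to 65%. All of this limits the consequence. It does not make the printed percentage the right one.

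Fourth, N may exceed the completer target. Someone given SP at Visit 1 of Part 2 who then leaves and is replaced is still SP-exposed, so the ratios for N=20 slightly overstate the dilution for a given k. This stands.

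**Conclusion.** The gap is real, but conditional. In any Part with at least one first-visit control failure, the SP-related AE percentages are computed on a set that includes people never given SP. Percentages for events attributed to SP are then N/(N+k) of their SP-exposed value: 0.92 or 0.95 for one failure at N=12 or N=20, and 0.80 at an assumed 20% failure rate. The failure rates and event counts are assumptions; the mechanism is not.

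A reader might infer more, and the documents do not support it:
- That every SP percentage is affected. With k=0 none is, and because the Parts are displayed separately, a failure in one leaves the other untouched.
- That the error always reassures. It does so for events attributed to SP, but not for overall AE incidence or under the missing-relationship rule.
- That failure rates well above 20% should be planned for. Four failures with 12 exposed (4/16 = 25%) or six with 20 (6/26 = 23%) would have to follow a passed screening test, and nothing in the documents suggests this.
- That later antagonist studies will rely on these AE rates. The stated purpose is a wheal and flare challenge model.

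This is a worthwhile, inexpensive correction to the SAP. No planned decision turns on it.

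**What to change.** In SAP section 3, add an SP-exposed set: Safety participants who received at least one SP injection. Then:
- Use it for both numerator and denominator of the SP-related AE summaries in SAP 4.5.2, so that the missing-relationship rule cannot bring in a never-exposed participant.
- Show SP-exposed incidence alongside the overall AE table on the Safety set.
- Keep the current Safety set for all-challenge, histamine-related and procedure-related events.
- Report the number of first-visit control failures in each Part.
- Record the addition in SAP 4.8, because Protocol 9.3 does not define such a set.

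The cost is one more analysis set and some extra columns or denominators. No new data are needed: the date and time of each SP administration are recorded (Protocol 6.4), and exposure is already listed by subject (SAP 4.5.1). If control failures occur, the percentages for SP-attributed events will look slightly less favourable.
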